Hospital length of stay will be collected from medical records and be defined as the number of days from surgical admission to hospital discharge.

Hospital readmission will be assessed as whether a patient is rehospitalized in an unplanned response to a surgical complication within 30 days of hospital discharge. Planned rehospitalizations will not be assessed as a hospital readmission.

Hospital physical function will be assessed using the AM-PAC test of inpatient physical activity and basic mobility³⁰.

Questionnaire/Psychological Outcomes Assessment:

Fatigue will be assessed using the Functional Assessment of Chronic Illness Therapy - Fatigue scale (FACIT-Fatigue), a validate measure of fatigue in cancer survivors³¹.

Health-related Quality of Life (HRQOL) will be assessed with the Functional Assessment of Cancer Therapy-General form (FACT-G)³². This form provides information on the physical, social, emotional, and functional well-being of patients with cancer.

Subjective psychological stress will be assessed with the Perceived Stress Scale (PSS)³³, which assesses *perceived stress* based on individual and environmental stressful events, focusing on experiences in the last month. *Depression* will be assessed using the Center for Epidemiologic Studies Depression Scale (CES-D)³⁴.

Prior physical activity level will be assessed with the Godin Physical Activity Questionnaire. This measure is a self-report estimate of leisure physical activity for the prior month. Prior physical activity level will be compared between groups and considered as a potential factor to control for in statistical analyses. This will only be collected at the first assessment.

Objective Stress Assessment:

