The potential participant population will be individuals who receive a diagnosis of borderline-resectable pancreatic cancer (adenocarcinoma), being treated at the University Hospital Cancer Center. These inclusion and exclusion criteria will apply to participants in both groups.

Inclusion Criteria: Recent (< 4 week) first diagnosis of a borderline-resectable pancreatic adenocarcinoma, assigned to receive neoadjuvant therapy and surgery at University of Colorado Cancer Center, physician clearance to participate in exercise program, and age 21-80 years.

Exclusion Criteria: Any significant comorbid conditions that would interfere with or preclude participation in an exercise intervention, including orthopedic conditions such as advanced osteoarthritis, mobility-limiting amputations or chronic injuries, or mobility-limiting acute orthopedic injuries; advanced rheumatoid arthritis; widespread chronic pain conditions such as fibromyalgia; pulmonary conditions such as chronic obstructive pulmonary disease, emphysema, interstitial lung disease, use of supplemental oxygen; known cardiovascular disease, uncontrolled hypertension, or new cardiac event within the past 6 months. Participants with a second cancer diagnosis at the time of enrollment will be excluded.

Sample size estimation: No studies have previously investigated the effects of preoperative exercise in patients with pancreatic cancer. In patients with lung cancer, a preoperative exercise program reduced hospital length of stay by 4 days compared to usual care⁴⁰. Based on this difference, with a SD of 3, 12 participants would be required in each the experimental and control groups ($\alpha = 0.05$, $\beta = 0.90$ ⁴¹). To account for overall attrition, groups will be increased by 3 participants each, based on a study of preoperative exercise after neoadjuvant treatment in patients with rectal cancer showing an overall attrition of 28%⁴². A total of **30 participants (15 per group)** will be recruited for this study.

C. Study Design and Research Methods

This is a prospective, non-randomized, parallel group, intervention control trial, patterned on a similar pilot study in patients with rectal cancer⁴².

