Recruitment: Participants will be recruited from the University Hospital Cancer Center. Patients with a recent diagnosis (< 4 weeks) of pancreatic cancer will be given information on the study by their treating physicians and asked if they would be interested in participating. If yes, physicians will have patients complete a HIPAA A form to provide study personnel with their name. Study personnel will access the patients' medical records to evaluate the inclusion/exclusion criteria. If these criteria are met, research personnel will meet with the

potential participant at the University of Colorado Cancer Center to provide information about the study. If patients are still interested in participating, the familiarization and possibly first visit will be scheduled. Participants will have the option of combining the familiarization session and Visit 1. All data collected during screening will be destroyed and recollected after obtaining written consent in patients choosing to participate. If the inclusion/exclusion criteria are not met after review of the health record, the patient will be contacted and the exclusion decision will be explained.

Group Assignment: Volunteers meeting the inclusion and exclusion criteria and willing to participate in the exercise intervention will be assigned to the exercise group. The standard of care, non-exercise control group will comprise volunteers who meet the inclusion and exclusion criteria but are unable to commit to participation in the exercise intervention for practical reasons (e.g. barriers in transportation or home location). The use of a non-randomized study design is to maximize patients participating in the exercise program to determine accrual rate, program adherence, and safety while still allowing a non-exercise control group.

Protocol:

[figure not shown]

Figure 1

Figure 1 shows the event timeline of the study, with time points of visits and intervention in relation to diagnosis and surgery. Written informed consent will be obtained by a study investigator during a familiarization period, where participants will have assessments and the exercise investigation explained in-depth. There will be four time points for data collection: pre-intervention (Visit 1), post-intervention and preoperative (Visit 2), 30-day postoperative (data retrieved from electronic health record), and follow-up (Visit 3).

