Thirty days after hospital discharge, the participants' electronic health record will be reviewed to retrieve data about initial hospital length of stay and 30-day unplanned hospital readmission. Visit 3 will be performed at approximately 6 weeks post hospital discharge. This is the time at which some patients may begin more chemotherapy or radiation treatment (adjuvant therapy), and Visit 3 will be performed prior to this to avoid confounding effects of the therapy.

Exercise Intervention: Participants will start the exercise program within four weeks of their diagnosis and decision to undergo neoadjuvant treatment and continue until surgery. Participants will continue to receive the standard medical care (described below) provided at UCCC. Individual exercise sessions in this program implement a "whole body" approach and consist of a 10-min cardiovascular warm-up and 50 minutes of cardiovascular endurance, resistance, and flexibility exercises (session components). Typical cardiovascular endurance exercises include walking on an indoor track or treadmill, stationary cycling, and stationary rowing. Resistance training includes exercises using body weight, free weights, and weight machines targeting increased strength of the large upper and lower extremity muscle groups and core stability. Flexibility exercises target major muscle groups activated during the exercise. Target intensity of exercise will be based on the American College of Sports Medicine (ACSM) recommendations for cancer survivors²: 40-85% heart rate reserve for cardiovascular endurance exercises; 60-70% one repetition maximum for resistance exercises; and a rate of perceived exertion of 12-16 on a 6-20 Borg scale for all activities.

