Exercise Adaptations: Prior to the start of exercise sessions, participants will be questioned on significant changes in symptoms or the presence of new symptoms (such as nausea or fever), which will be used to modify the exercise session (intensity and components) for that day to allow maximum symptom-limited participation. Participants will be encouraged to complete three sessions per week for at least eight weeks during neoadjuvant therapy. Exercise intensity, components, and time will be recorded for each exercise session to guide the exercise specialist in making appropriate exercise adjustments (progression, maintenance, or reduction). Exercise programs have been found to be safe in cancer survivors, even during life-threatening treatments², but safety has not been investigated specifically in the current population. Common risks may include muscular fatigue and soreness, as well as transient increases in treatment-related symptoms. Rarer risks include the possibility of injury due to unknown bone metastases or acute cardiac events. Intensity and acute changes in symptoms will be closely monitored to decrease these risks.

Participants will schedule their sessions with the exercise specialists administering the program, typically taking place between 8AM and 4PM, Monday through Friday, at the

Anschutz Center for Health and Wellness. Adherence will be measured as the percent of scheduled sessions attended. Exercise sessions will also be individualized to participants on a day to day basis, with time and intensity not exceeding that listed above. Prior to the start of exercise sessions, participants will be questioned on significant changes in symptoms or presence of new symptoms (such as nausea or fever), which will be used to modify the exercise session for that day. Exercise intensity, type, and time will be recorded for each exercise session.

Standard Care: Participants in the Standard Care group will receive no exercise intervention, but will continue to receive standard follow-ups, treatments and services from their oncology team. The services that participants receive as standard care include their medical care, symptom control, social worker support, and nutrition.

Participants in all groups will receive \$50 reimbursement for each Visit completed, totalling \$150.00 for all three Visits.

D. Description, Risks and Justification of Procedures and Data Collection Tools:

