Potential Problems and Solutions: Given that no previous studies of preoperative exercise programs exist in patients with pancreatic cancer, the power analysis for the current study was based on the outcomes of a study of preoperative exercise in patients with lung cancer. It is possible that the estimated sample size here will not provide enough power to detect differences in postoperative outcomes. Regardless of statistical significance, outcomes from this study will provide the basis to allow future studies in this population that are adequately powered. Study groups will not be randomized, resulting in a potential selection bias and baseline differences. The decision to design the study as a non-randomized trial was made to improve recruitment for the target patient population and the short duration of the funding period. Analysis of the number of participants who are willing and able to participate in an exercise intervention at the AHW will determine if a randomized trial is feasible and allow a better estimate of a realistic enrollment period. We will interpret our enrollment activity as

follows: if less than 70% of anticipated enrollment is achieved, we will conclude that additional study sites will be needed to enroll sufficient numbers of patients treated with neoadjuvant therapy for pancreatic cancer for formal hypothesis testing in a RCT.

The individualized nature of the exercise program precludes rigorous control of exercise components between participants. An individualized exercise program may increase adherence and will allow adaptability to acute changes in the patients' health status due to treatment- or disease-related symptoms. The neoadjuvant therapy period will vary between participants, resulting in a variable duration of the exercise intervention. The duration of exercise must remain variable to avoid deconditioning that would be caused by a long lapse between the end of the exercise intervention and surgery. Most patients complete 16 weeks of neoadjuvant therapy before surgery, which will result in a typical exercise intervention lasting 12 weeks. We will record the duration of exercise training and neoadjuvant therapy and test these factors as covariates in the analyses of the fitness, function, and stress outcomes.

F. Data Analysis Plan:

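### Readmission is taken only from a health record review 30 days after discharge, while controls may be the patients who live further away, so readmissions to other hospitals could be missed more often in controls

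*Combined protocol and SAP*

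**What the plan says.** Section IV.A (Postoperative outcomes) counts a patient as readmitted if "rehospitalized in an unplanned response to a surgical complication within 30 days of hospital discharge"; planned admissions are excluded. Nothing limits the count to the operating hospital.

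Section IV.C (Assessments) gives the source. Thirty days after discharge, the "electronic health record will be reviewed to retrieve data about initial hospital length of stay and 30-day unplanned hospital readmission". The list of time points under Protocol in the same section also names only the record: "30-day postoperative (data retrieved from electronic health record". The next study contact is later: "Visit 3 will be performed at approximately 6 weeks post hospital discharge". The assessments listed for that visit include no question about admissions.

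Section IV.C (Group Assignment) makes the exercise group the eligible volunteers who are willing to exercise. Controls are those "unable to commit to participation in the exercise intervention for practical reasons (e.g. barriers in transportation or home location".

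Section IV.F (Aim 2, Hypothesis 2) compares readmission between groups with Fisher's exact test and expects fewer readmissions with exercise.

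**The concern.** A chart review finds what is in the chart. The documents do not say whether this record shows admissions to other hospitals. A patient who lives far away or has trouble travelling may go to a nearer hospital with a complication, and the protocol names those two characteristics as reasons for being a control. Exercisers are people able to come to the campus for supervised sessions, three a week being encouraged. The chance that a readmission is recorded may therefore differ by group because of how the groups are formed.

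This is a different problem from the selection bias and baseline differences acknowledged in section IV.E. Those concern who is in each group; this concerns whether the outcome is seen. Using differing baseline variables as covariates (section IV.F) cannot restore events that were never recorded.

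Under-counting in controls works against exercise: it could hide a benefit or suggest harm. The rates matter beyond this trial, because section IV.E says that, significant or not, "outcomes from this study will provide the basis to allow future studies in this population that are adequately powered". A control rate that is too low would carry into that planning.

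**Working it through.** **The plan's own figures.** The documents give no readmission rate, capture rate or power for readmission. The 12 per group in section IV.B is for length of stay (difference 4 days, SD 3). It reproduces with the two-sided normal approximation: 2 × (1.960 + 1.282)² × 3²/4² = 11.8, rounded up to 12. It has no bearing on readmission. Index length of stay comes from the operating center and is not affected by this concern.

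**Inputs from the documents.** 15 per group (IV.B); review at 30 days after discharge and Visit 3 at about 6 weeks after discharge (IV.C); Fisher's exact test (IV.F).

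**Inputs that are assumptions.** Let *p* be the true readmission rate, first taken as equal in both groups, and *m*C and *m*E the shares of events missed in controls and exercisers. The values below are illustrations.

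**Step 1: false difference when the true rates are equal.** The observed rates are *p*(1 − *m*E) and *p*(1 − *m*C), so the false excess with exercise is *p* × (*m*C − *m*E).

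| *p* | *m*E | *m*C | False excess (points) |
|---|---|---|---|
| 30% | 0 | 0 / 10% / 30% / 50% | 0 / 3 / 9 / 15 |
| 30% | 10% | 10% / 30% / 50% | 0 / 6 / 12 |
| 30% | 20% | 20% / 30% / 50% | 0 / 3 / 9 |
| 15% | 0 | 0 / 10% / 30% / 50% | 0 / 1.5 / 4.5 / 7.5 |

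In patients, the largest values are 15 × 0.15 = 2.25 and 15 × 0.075 = 1.1. When capture is equal the bias is zero.

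**Step 2: a real benefit partly hidden.** Take true rates of 10% with exercise and 30% in controls, a 20-point difference, with 95% of exerciser events captured.

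- 80% of control events captured: 0.10 × 0.95 = 9.5% against 0.30 × 0.80 = 24%, a difference of 14.5 points.
- 60% of control events captured: 9.5% against 0.30 × 0.60 = 18%, a difference of 8.5 points.

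At 15 per group, the chance that Fisher's test favours exercise is 14.9% with complete capture, 8.0% in the first case and 3.0% in the second.

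**Step 3: power with complete capture.** Exact binomial enumeration, two-sided 0.05, 15 per group: 20% against 30% gives 0.040; 15% against 30% gives 0.078. The test will rarely be significant whatever the capture, so the effect falls mainly on the reported rates. Single events can still matter: 0 of 15 against 5 of 15 gives p = 0.042, and 0 of 15 against 4 of 15 gives p = 0.100.

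**Step 4: timing.** Visit 3 is at about 6 × 7 = 42 days after discharge, the review at 30 days. The review therefore precedes the visit by about 12 days, and no later check of the record is planned.

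**The case against.** The bias needs several conditions, none of them documented: more controls than exercisers living far away, those controls being admitted elsewhere, the record not showing it, and no note reaching the chart before the review. The barriers are only examples, and being unable to attend three weekday sessions a week does not mean using another hospital. All participants are "assigned to receive neoadjuvant therapy and surgery at University of Colorado Cancer Center", attend the same study visits, and controls "will continue to receive standard follow-ups, treatments and services from their oncology team". There are other contacts: symptoms are asked about at testing sessions, adverse events are reported, and each participant gives a clinical provider's contact details (section IV.D). The consent form is not among the documents reviewed, so an authorization to obtain outside records may exist. The 15-point figure requires half of control events to be missed and none in exercisers. Even that is below one standard error of the difference: √(2 × 0.30 × 0.70 / 15) = 16.7 points, or 13.0 points at a true rate of 15%. Readmission is neither the primary fitness outcome nor the basis of the sample size, and the plan promises cautious interpretation.

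Much of this stands. The size is unknown and may be zero, shared surgery and follow-up will bring some outside admissions into the chart, and sampling error is larger than the bias in this trial. Nor does the text say that the chart is closed at day 30. But the symptom check, adverse event reporting and provider contacts are not questions about admissions, and none is named as a source for this outcome. A standard error shows sampling noise; it does not reveal unequal capture, which a reader of the rates would have no means of detecting.

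**Conclusion.** The concern holds as a possibility that the plan leaves open; the documents do not show that bias will occur. The definition covers any hospital, the only stated source is one chart review at 30 days after discharge, and the assignment rule may link group to where patients are readmitted.

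Under the illustrative assumptions the false excess with exercise runs from 0 to 15 points at a true rate of 30%, and from 0 to 7.5 points at 15%. The upper ends require half of control events to be missed and none in exercisers. With power of about 4–8% under the assumed rates, the consequence is mainly for the descriptive rates and the later studies built on them. Confidence is medium, because the visibility of outside admissions and the distance controls live from the center are not documented. The change is worth making because it is cheap and would also show whether capture differed.

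**What to change.** Keep the record review and add a second source, identical in both groups:

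1. At Visit 3, after the 30-day window has closed, ask every participant one standard question: any hospital admission since discharge, at any hospital, and on what date.
2. Put the same question by phone to participants who miss Visit 3.
3. For any reported admission not in the record, request the outside record and check date, cause and unplanned status against the definition in section IV.A.
4. Count readmissions from both sources in both groups, and report by group how many were found only by the question.

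The cost is one question at a visit already scheduled, a few phone calls and an occasional records request among 30 participants. The outcome definition and visit schedule do not change.

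A separate wording correction: the time-point list in section IV.C dates this data point from surgery, while sections IV.A and IV.C (Assessments) count from discharge. Relabel it as 30 days after hospital discharge.

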The timeline for this protocol is estimated at 2 years. Data collection (participant recruitment and intervention) is estimated at 1 - 1.5, after which data will be analyzed and manuscripts prepared.

Data Analysis and Anticipated Outcomes: Groups will be compared on demographic variables such as age and gender. Variables that differ significantly will be included in planned analyses as covariates. Statistical significance will be defined as $\alpha \leq 0.05$, however, results will be interpreted cautiously as is warranted for pilot studies⁴⁴. As we expect to be underpowered to test for statistical interactions, multiple tests will be used to assess differences in baseline measures, change scores, and postoperative outcomes between groups. Change scores will be calculated as the difference between Visit 2 and Visit 1. Groups will be compared using non-parametric exact k-sample permutation tests, which are well suited for small sample sizes as they do not rely on typical normal-theory methods⁴⁵.

Aim 1: The feasibility of implementing this intervention will be assessed by quantifying the accrual rate of patients willing and able to participate in the preoperative exercise intervention and individual patients' adherence to the prescribed exercise program (percentage of scheduled sessions attended). Safety will be determined by the number of non-serious and serious adverse events and relatedness of the events to exercise, as described by COMIRB.

Aim 2: Hypothesis 1 – Baseline physical fitness and function measures and change scores will be compared between groups using exact k-sample permutation tests. We anticipate a significant difference in the changes from Visit 1 to Visit 2, with the Exercise group demonstrating maintained or improved physical fitness and function compared to the Control group, with no differences in baseline measures. A secondary analysis will be used to describe the trajectory of changes in physical function from visits 1, 2, and 3.

Hypothesis 2 – Postoperative outcomes will be compared with exact k-sample permutation tests (hospital length of stay) or Fisher's exact tests (hospital readmission) between the Exercise and Control groups. We anticipate the Exercise group to have a significantly lower hospital length of stay and occurrence of hospital readmission compared to the Control group.

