Exploratory Aim: Hypothesis 1 – Baseline psychological stress and systemic inflammatory status measures and change scores will be compared between groups using exact k-sample permutation tests. We anticipate a significant difference in change scores, with the Exercise group demonstrating decreased (improved) psychological stress and improved systemic inflammatory status (decreased CRP, IL-6, sTNFR1 and IIS; increased IL-10) compared to the Control group, with no differences in baseline measures.

Hypothesis 2 – Spearman correlations will be performed between preoperative measures of psychological stress and systemic inflammatory status and postoperative variables. We

anticipate a significant negative correlation between psychological stress and systemic inflammatory status and postoperative outcomes, with lower levels of stress and inflammation associated with improved outcomes in all participants.

G. Summarize Knowledge to be Gained:

Aim 1: The feasibility of future, larger scale implementation of the preoperative exercise program will be assessed primarily by patient adherence to the program, demonstrating patients' ability and willingness to complete the program. The future study of the intervention will be assessed through the measurement of patient accrual, which will provide a reference for the necessary time frame of future studies.

Aim 2: The analyses performed in this aim will reveal 1) how a preoperative exercise intervention affects physical fitness and physical function prior to and after surgery, and 2) whether a preoperative exercise program is associated with improved postoperative outcomes in patients with pancreatic cancer undergoing neoadjuvant treatment. These analyses will also illustrate typical changes in measures of physical fitness and physical function through analysis of the Standard Care group.

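### Aim 1 adherence is attendance at scheduled sessions only, so on its own it can overstate how much of the encouraged exercise programme was completed

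*Combined protocol and SAP*

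**What the plan says.** The measure is set in section IV.C, Exercise Adaptations: "Adherence will be measured as the percent of scheduled sessions attended". Section IV.F, Aim 1, repeats it as "adherence to the prescribed exercise program (percentage of scheduled sessions attended".

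Three statements in section IV.C govern what gets scheduled:

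- On booking: "Participants will schedule their sessions with the exercise specialists administering the program".
- On amount: "Participants will be encouraged to complete three sessions per week for at least eight weeks during neoadjuvant therapy".
- On duration: "Participants will start the exercise program within four weeks of their diagnosis and decision to undergo neoadjuvant treatment and continue until surgery".

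No section gives a minimum number of sessions to book, says whether bookings are made week by week or as a series, or says how bookings left open when a participant stops are counted.

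On interpretation, section IV.G, Aim 1, says the feasibility of wider implementation "will be assessed primarily by patient adherence to the program" and takes this to show patients' "ability and willingness to complete the program".

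On data, section IV.C states: "Exercise intensity, type, and time will be recorded for each exercise session". Section IV.E adds that the lengths of training and of neoadjuvant therapy will be recorded, for use as covariates in the fitness, function and stress analyses.

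**The concern.** The plan infers completion of a programme but measures attendance at appointments. The two agree only if the appointments made amount to the programme, and nothing in the protocol ensures that.

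Several ordinary events reduce the exercise done without creating a missed booking. A participant may book fewer sessions in bad weeks, choose to stop, be discontinued as no longer physically capable (section IV.D, Data Safety and Monitoring), or pause while awaiting clearance after a medical emergency (section IV.D). The people for whom the programme proved least feasible can then contribute few sessions to the denominator and still show a high percentage. Someone assigned to exercise who never books gives 0/0, which the definition does not cover.

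What is at stake is how the figure is read. A high percentage could be carried into the planning of a larger study as evidence that patients complete the programme, when some stopped early or scheduled little.

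**Working it through.** The plan states no adherence target or expected value, so there is no figure to reproduce. The check compares the planned ratio with attendance against the protocol's own encouraged minimum.

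**Inputs**
- Planned ratio = attended / scheduled (sections IV.C and IV.F).
- Encouraged minimum = 3 per week x 8 weeks = 24 sessions (derived from section IV.C).
- Typical training period = 12 weeks (section IV.E). At 3 per week this would be 36 sessions. That figure is an assumption, used only to illustrate a long series of bookings.
- Planned exercise group = 15 (section IV.B).
- The booking and attendance counts below are illustrative assumptions.

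**Single participants**

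| Case | Scheduled | Attended | Planned ratio | Attended / 24 |
|---|---|---|---|---|
| A. Full minimum | 24 | 24 | 100% | 100% |
| B. Misses some bookings | 24 | 18 | 75% | 75% |
| C. Books less | 16 | 16 | 100% | 67% |
| D. Books week by week, stops | 12 | 12 | 100% | 50% |
| E. Books little | 8 | 8 | 100% | 33% |
| F. Series of 36 booked, stops after 12 | 36 or 12 | 12 | 33% or 100% | 50% |
| G. Series of 36 booked, attends 24 | 36 | 24 | 67% | 100% |
| H. Six-week period, 3 x 6 = 18 | 18 | 18 | 100% | 75% |
| I. Never books | 0 | 0 | 0/0, undefined | 0% |

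**What the cases show**
- In B the planned ratio falls as it should, because the missed sessions were booked. In C, D and E it stays at 100% while attendance against 24 drops to 67%, 50% and 33%.
- The ordering can reverse. B did 18 sessions and scores 75%. E did 8 and scores 100%.
- F depends on an unstated rule: 12/36 = 33% if open bookings count as missed, 12/12 = 100% if they are removed. Fixing that rule settles F but not D, where no bookings were open.
- G shows the planned ratio doing something that a 24-session criterion does not: it registers the 12 missed bookings.
- H shows the weakness of the 24-session criterion, which marks down a participant whose preoperative period was short.

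**Group level**
Suppose k of the 15 behave as in D and the other 15 - k as in A. The mean planned ratio is 100% for every k. The proportion reaching 24 sessions is (15 - k)/15:
- k = 0: 15/15 = 100%
- k = 3: 12/15 = 80%
- k = 5: 10/15 = 67%

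Each such participant moves completion by 1/15 = 6.7 percentage points and the planned figure by nothing. The value of k is unknown.

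**The case against.** The strongest reply is that section IV.F ties the ratio to the prescribed programme. If scheduled means prescribed, every encouraged session is in the denominator and unbooked sessions count against the participant. Sessions are also arranged with the specialists, so the participant does not set the denominator alone. This reading is possible, but no section says that all encouraged sessions are booked. Section IV.C points the other way, since participants do the scheduling and the amount is only encouraged. Even with full advance booking, bookings left open at stopping have no rule.

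The second reply concerns weight, and it stands. Adherence is called the primary consideration only in section IV.G. The Aim 1 objective in section I and the analysis in section IV.F list accrual, adherence and safety without ranking them. Section IV.E rests the feasibility of a randomized trial on how many patients can and will take part, and its only numerical rule, 70%, concerns enrolment. A reader might infer that a wrong go-ahead decision could follow from the adherence figure. The documents do not support that, because no decision is tied to it.

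Third, the underlying data are already collected, and volunteers who cannot commit for practical reasons go to the control group (section IV.C, Group Assignment). Case I may therefore be uncommon. Both points stand. They make the problem smaller and the remedy cheaper, but neither puts completion into the Aim 1 summaries.

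A reader might also want attendance divided by three per week for the whole period up to surgery. The protocol does not state that rate beyond eight weeks. Someone who met the encouraged minimum over a 12-week period would read 24/36 = 67%, so this should not stand as an equal summary.

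**Conclusion.** The point holds in a limited form. The planned ratio is a legitimate measure of attendance at bookings, but it does not by itself support the inference about completion in section IV.G. It can read 100% for a participant who did half of the encouraged minimum, and it is undefined for one who never booked.

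This rests on 24 sessions as the encouraged minimum, which follows directly from section IV.C, and on the absence of any stated requirement to book them. The size of any overstatement in this trial is unknown: it depends on booking practice and on how many participants stop or book little. It would be wrong to infer that the reported figure will be inflated, or that the ratio should be replaced. If all encouraged sessions are booked as a series and open bookings count as missed, the gap largely closes.

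The consequence is confined to a descriptive Aim 1 figure that may be read as more than it is. Repairing it is a cheap improvement.

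**What to change.** In sections IV.C and IV.F, keep the ratio of attended to scheduled sessions, and state that bookings left open when a participant stops count as missed.

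Beside it, among the Aim 1 summaries, report the following for everyone assigned to the exercise group, including those who stop, are discontinued or never book (counted as 0 sessions):

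- (a) the number and percentage who attended at least 24 sessions;
- (b) total sessions attended, weeks of training, sessions per week of training (for those who started), and the numbers who stopped early and who never started.

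Also state how many had fewer than eight weeks before surgery, since (a) marks them down through no fault of adherence. Show separately any participants for whom a start or surgery date is missing.

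The cost is a few lines of text and a few summary rows. Session records and training duration are already planned, and the surgical admission date is needed for length of stay. It may not be available for participants discontinued from the study. The resulting figures may look less favourable. The change affects measurement and reporting only and leaves the exercise schedule as it is.
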